1.0 Study Design and Methods

Study Design

To address the study objectives, a pilot randomized controlled trial will be conducted.

Study population:

Group 1: Veterans

A convenience sample of Veterans , who are screened and diagnosed with Parkinson's disease (PD) and mild cognitive impairment in the executive function domain will be enrolled. Targeted enrollment for the intervention is 45; they will be randomized to one of three groups: CCT+PRIIS (n=15), CCT+PRIIS control (n=15) or CCT control +PRIIS control (n=15).

Group 2: Knowledgeable Informants

We will also enroll knowledgeable informants/caregivers of the enrolled Veterans. Thus, we will be enrolling civilians (however it is possible that caregiver could be a Veteran and this is acceptable). The purpose for enrolling a caregiver is to obtain their perspective on functional changes related to cognitive impairment in the Veteran living with PD. To obtain their perspective, they will complete the PD-Cognitive Functional Rating Scale (PD-CFRS) at three different time points during the study. The planned activities for the caregiver are the following: consent, demographic form, PD-CFRS at three different time points. The consent form, demographic form and PD-CFRS will be completed at their first visit. We will mail them the form when their Veteran completes the RCT, we will mail them the form again one month later. A knowledgeable informant/caregiver is not required in order for the Veterans to enroll. Targeted enrollment is 45, however we anticipate having to enroll 60 civilians due to Veterans being withdrawn – and thus the associated civilian will need to be withdrawn.

Below we list the inclusion and exclusion criteria for both Veterans and Knowledgeable Informants.

Group 1: Veterans

In general, eligibility criteria target Veterans with idiopathic PD and not other forms of parkinsonism. Thus, only Veterans older than 50 with PD diagnosed according to UK Parkinson's Disease Society Brain Bank

Diagnostic Criteria will be eligible. PD medication can influence cognitive function, thus, only participants receiving stable medication (i.e., no changes in medication or dose for the past month) and who are expected to remain on stable medication for the duration of the RCT will be eligible.

Inclusion criteria for Veterans:

- Diagnosis of PD as determined by the UK Parkinson's Disease Society Brain Bank Diagnostic Criteria⁴⁶
- age 50 and older

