Repeated measures/study outcomes are included in a standardized battery of test that will be repeated at baseline, endpoint and follow-up. The battery is expected to take approximately 130 minutes to complete.

Tests administered during screening (e.g., the BDI-II, MoCA, BAI, and HVLT, Memory for Intentions Test, and Modified Fatigue Impact Scale) will not be replicated at baseline, but are included in Table 3 below to indicate it is a repeated measure.

Table 3: Repeated Measures Assessment Tools used in the RCT			
Assessment Name (Abbreviation)	Outcome	Construct measure	Time to complete (min)
NIH-EXAMINER components:	1° (composite score of 7 tests listed below)	Executive function	29 total
Dot counting	2°	Working Memory	7
1-back			5
2-back			5
Flanker	2°	Cognitive Control	5
Set Shifting			5
Letter	2°	Verbal Fluency	1
Category			1
Hopkins Verbal Learning Test-Revised (HVLT)	2°	Memory	10
Symbol Digit Modalities Test (SDMT)	2°	Processing speed	5
The Memory for Intentions Test (MIST)	2°	Prospective memory	15
Monetary-Choice Questionnaire	2°	impulsivity	10
Parkinson's Disease-Cognitive Functional Rating Scale (PD-CFRS)	2°	Real-life function	5
The Activity Measure for Post-Acute Care™ (AM-PAC™) –Applied Cognition questionnaire	2°	Real-life function	10
Timed instrumental activities of daily living (iADL)	2°	Real-life function	15
Beck Depression Inventory-II	2°	Depression	10
Beck Anxiety Inventory	2°	Anxiety	10
Starkstein Apathy Scale	2°	Apathy	5
Montreal Cognitive Assessment	2°	Global Cognition	10
Epworth Sleepiness Scale	2°	Sleepiness	5
Modified Fatigue Impact Scale	2°	Fatigue	5
			Total Time: 144 minutes

Phase 4: Intervention

Participants will be randomized to one of three groups: CCT+PRIIS (n=15), CCT+PRIIS control (n=15) or CCT control +PRIIS control (n=15) and issued a VA iPad to take home and complete the study intervention.

Participants and researchers who are administering and scoring outcome measures will be blinded to group assignment. Effectiveness of blinding will be evaluated by using data collected from mid-point and endpoint questionnaires that assess perception of training intervention⁶⁹. The PI will oversee the RCT and coordinate research procedures and thus will not be blinded to treatment assignments. [name], who will be blinded to group assignments, will coordinate sensitive aspects of the study that require blinding.

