All participants will complete the assessments listed in Table 3 in a private room with trained research staff at Hines. A semi-structured interview will also be conducted by trained research staff. This interview will take approximately 30 minutes and discussion will focus around feasibility of participating in the study, perception of training for the 2 interventions, usefulness of the weekly cognitive coach calls, and guess at treatment group allocation. We will audiotape this part of the session. The option to consent to audiotaping is included in the veterans's consent form

Phase 6: Follow-up

Follow-up Behavioral Assessments:

One month after the last intervention session, all participants will complete the assessments listed in Table 3 in a private room with trained research staff at Hines.

Unblinding:

Participants will be unblinded after the last participant completes the study. A letter will be mailed to the Veterans.

Knowledgeable informants/caregivers

Knowledgeable informants/caregivers enrolled in the study will be administered the PD-CFRS. Data from the informant will be collected at baseline in person and, to reduce burden of data collection, end-point and follow-up surveys will be mailed to informants for completion. Filling out this form three times (along with an initial demographic form) are the only research procedures performed by the knowledgeable informants/caregivers.

COMPENSATION FOR PARTICIPATION IN RESEARCH ACTIVITIES

Veteran participants will be compensated \$120 for completing all research procedures in this study. Participants will receive \$30 after completing the 2-3 hour long diagnostic confirmation screen. Participants will receive \$30 after completing baseline neuropsychological assessments, \$30 after completing endpoint neuropsychological assessments and \$30 after completing follow-up neuropsychological assessments.

Payment Procedures if screening and/or assessments are completed Hines VA: they will be reimbursed \$30 direct deposit via electronic funds transfer (EFT).

Knowledgeable informants/caregivers will not receive compensation.

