5.0 Data Analysis

All test administrators will undergo the same training. Data will be cleaned and tested for normality (if normality tests fail, appropriate transformations will be made), and proper missing data imputation techniques will be used. Test for multicollinearity will be made. The 3 treatment groups will be characterized using descriptive statistics for demographic factors, disease-related variables, and medication use. Groups will be examined for comparability according to the descriptive variables using ANCOVA and mixed-effects model with random subject effects. For ANCOVA, type I error rate ($\alpha=0.05$) will be adjusted for multiple comparisons using Bonferroni corrections.

Neuropsychological Data Analytical Approaches. For Aims 2 and 3, data will be analyzed using a two-level longitudinal mixed effects model with random subject effects to incorporate correlation of measurements nested within the same subject. Covariates will include medication dose, anxiety, apathy, and depression level. Parameters will be estimated using measurements from baseline, endpoint, and follow-up. The group by time interaction parameter will be used to examine the difference of the trends between the three groups. Significance of this parameter will indicate that treatment is efficacious in terms of EF over time when adjusted by covariates. To assess immediate effects of CCT, an experiment group contrast will be formed using test score means at baseline and endpoint and a control group contrast will be made with those same types of means. To assess sustainability of CCT effects, contrasts using means of test scores at endpoint and follow-up will be made for each group. Estimates of variance components from mixed-model analysis will be used to calculate test statistics. Data analysis will be performed using SAS 9.3 Proc Mixed. This modeling process will be reported for each outcome of interest in Aims 2 and 3. Potential moderators of the effects of the CCT will be explored through Pearson correlations and regression analyses. Factors include, age, age at PD onset, disease duration, MoCA score, depression, anxiety, apathy, L-dopa equivalent dose, PD-MCI subtype diagnosis,

scores on training perception, prior computer use and cognitive training. Co-morbidities and medications will be considered as confounders.

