MCID for the NIH-EXAMINER executive composite score will be computed using two anchor-based MCID approaches. First, a within patient score change approach will be used, which defines MCID as the mean change between the outcome scores (NIH EXAMINER Executive composite score) of a group of patients selected per their answers. Second, a sensitivity- and specificity-based approach will be used. This anchor-based approach is useful to calculate the threshold that allows for the best discrimination between groups of patients. The outcome score that produces the greatest and most balanced sensitivity and specificity for discriminating patients with minimal change from patients without any change will be considered as the MCID. Used in conjunction with MCID estimations, sensitivity is the proportion of the patients having change on the external criterion (PD-CFRS) and whose outcome score (NIH EXAMINER Executive composite score) change exceeds the threshold MCID value. Similarly, specificity is the proportion of subjects without any changes on the external criterion (PD-CFRS) and whose outcome changes are below the threshold MCID value. Full, partial and non-responders will be defined using the MCID in both the sham and active rTMS groups (i.e., full = > 1 MCID, partial= 1 MCID, non= < 1 MCID).

The psychometric properties of the PD-CFRS (both self-report and informant report assessed separately) will be assessed using the Rasch model (i.e., construct validity) and concurrent validity will be examined using traditional correlational methods (i.e., concurrent validity with NIH-EXAMINER). For the PD-CFRS, the interrater agreement between self- and informant ratings will be calculated using the Corrected Discrepancy score, which is a rigorous measure correcting for between-subject differences in actual level of scoring.

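### Informant PD-CFRS moves from site visit to mail after baseline, so within-arm informant change from baseline and post-baseline self-informant agreement cannot be separated from setting

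*Combined protocol and SAP*

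**What the plan says.** Two parts of Section 1.0 describe the informant's schedule, and they agree. Under Group 2: Knowledgeable Informants, the baseline form is done on site: "The consent form, demographic form and PD-CFRS will be completed at their first visit". The later forms go by post: "We will mail them the form when their Veteran completes the RCT, we will mail them the form again one month later". The Knowledgeable informants/caregivers paragraph repeats this and gives the reason: "Data from the informant will be collected at baseline in person and, to reduce burden of data collection, end-point and follow-up surveys will be mailed". It describes a single instrument throughout: "Filling out this form three times (along with an initial demographic form) are the only research procedures performed by the knowledgeable informants/caregivers". No difference between arms is stated.

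For the Veteran, Phase 5: Endpoint says: "All participants will complete the assessments listed in Table 3 in a private room with trained research staff at Hines". Phase 6: Follow-up uses the same terms. Table 3 includes the PD-CFRS as a secondary outcome for real-life function, without saying whether the self or the informant version is meant. Phase 3: Baseline data collection does not name the setting, but the telephone script in Phase 1 promises four site visits. That matches screening, baseline, endpoint and follow-up.

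Section 5.0 bases efficacy on a between-arm test: "The group by time interaction parameter will be used to examine the difference of the trends between the three groups". It also plans contrasts for each group, baseline to endpoint for immediate effects and endpoint to follow-up for sustainability. PD-CFRS change is the external criterion for the MCID of the NIH-EXAMINER composite, with no rater named. For the two raters, "the interrater agreement between self- and informant ratings will be calculated using the Corrected Discrepancy score"; no visit is named. Setting or mode of completion is not mentioned in Section 5.0.

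**The concern.** The informant's setting changes at the boundary between baseline and the post-baseline assessments, for every informant at once, and for only one of the two raters. Setting is then fully aliased with time in informant change from baseline, and with rater in self-informant agreement at endpoint and follow-up. Once the baseline forms are in, no analysis can separate them.

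Three planned uses are exposed, two of them conditionally:

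- the per-group baseline-to-endpoint contrast, if informant scores are analysed as an outcome;
- the Corrected Discrepancy score, if computed at endpoint or follow-up;
- the MCID anchor, if it is informant-rated. Randomisation gives no protection here, because patients are classified individually as changed or unchanged. The resulting MCID is then used to define full, partial and non-responders.

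**Working it through.** The plan gives no sample size, power or effect figure for the informant PD-CFRS, so there is no stated figure to reproduce. The check is algebra plus an illustration.

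**Step 1: where a shift goes.** Let a mailed form move the informant's score by *m*, equally in all arms.

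| Quantity | Bias |
|---|---|
| Informant change, baseline to endpoint (or to follow-up), within an arm | *m* − 0 = *m* |
| Informant change, endpoint to follow-up | *m* − *m* = 0 |
| Between-arm difference in change (group by time) | *m* − *m* = 0 |
| Self minus informant, baseline | 0 |
| Self minus informant, endpoint and follow-up | −*m* |

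The last two rows use the simple difference, because the documents give no formula for the Corrected Discrepancy score. They also take the Veteran's baseline as in person, which is inferred from the four site visits.

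**Step 2: what a shift could do.**

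Inputs from the documents: 15 Veterans per arm in three arms (Section 1.0). Informants are optional, so 10 per arm is also shown.

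Assumed inputs:

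- *m* of 0.2, 0.3 or 0.5, with score SD 1;
- within-person correlation ρ of 0.5 to 0.7;
- two-sided 5% tests (Section 5.0 states 0.05 for the ANCOVA);
- no true change.

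The SD of a change score is √(2(1 − ρ)): √1.0 = 1.00 at ρ = 0.5 and √0.6 = 0.77 at ρ = 0.7. The noncentrality of the within-arm t-test is *m*√n / SD of change. For *m* = 0.3 and n = 15 it is 0.3 × 3.87 / 1.00 = 1.16, or 0.3 × 3.87 / 0.77 = 1.51.

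False-positive rates from 20,000 simulated trials per setting (lower figure ρ = 0.5, upper ρ = 0.7):

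| *m* (score SD) | Within-arm, n = 15 | Within-arm, n = 10 |
|---|---|---|
| 0 | 5% | 5% |
| 0.2 | 11–15% | 9–11% |
| 0.3 | 19–28% | 13–19% |
| 0.5 | 44–64% | 30–44% |

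In every setting the endpoint-to-follow-up contrast and the group-by-time test (one-way ANOVA of change scores) stayed at about 5%, as the algebra predicts.

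**The case against.** There is a fair case for leaving this alone.

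- **The documented change is one of setting.** The informant fills out the same form each time. The documents do not say that staff clarify items at baseline, nor that the Veteran takes part at home. Section 1.0 does use the word administered as well, so the degree of supervision is open. This stands: the effect may be small, and nothing in the documents shows that it exists.
- **Mailing is deliberate.** It spares informants who are not compensated, and it is applied alike in all arms. This also stands, and it is why the fix keeps the mailing.
- **The efficacy test is safe.** A common shift cancels in the group-by-time interaction, and likewise when the experimental contrast is compared with the control contrast. Only a within-arm contrast read alone is exposed. What could still affect the arms differently is a mode effect that varies by arm, or unequal return of mailed forms.
- **The MCID anchor is probably self-report.** The first MCID approach groups patients by the answers they give, and an optional informant could not supply an anchor for every Veteran. The second approach names no rater, so the risk is conditional.

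A reader might infer more than the documents support. They do not show that all informant change and all agreement are confounded: endpoint-to-follow-up change is mail to mail, and baseline agreement has no visit-versus-mail difference. Section 5.0 plans no single test of informant change pooled over all 45, so error rates for such a test are not relevant. It plans no analysis of change in discrepancy either. Nor can one say that unchanged Veterans would be counted as changed, since neither the direction of a shift nor the threshold is known, and a shift could equally hide real change.

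**Conclusion.** The point holds in a limited form. Informant change from baseline within an arm, and self-informant agreement at endpoint and follow-up, cannot be separated from the move from site to mail. The MCID anchor shares the problem only if it is informant-rated. The trial's main between-arm inference is untouched.

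The size is unknown. The 11% to 64% range for 15 informants per arm shows what shifts of 0.2 to 0.5 SD would do under the assumptions above; it is not evidence that such shifts occur. The conclusion also assumes that the Veteran's baseline rating is in person, and that informant scores are analysed as an outcome, which Table 3 leaves open. It is a minor, inexpensive improvement.

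**What to change.** Procedure, Section 1.0:

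- At the first visit, have the informant self-complete the same paper PD-CFRS that will be mailed later, unassisted, apart from the Veteran, and with the same printed instructions.
- On every form, ask that it be completed without the Veteran, and record the completion date.

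Analysis, Section 5.0:

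- Make baseline the main visit for the Corrected Discrepancy analysis. Label any endpoint or follow-up agreement as mixing rater with setting.
- Name the Veteran's self-report PD-CFRS as the MCID anchor.
- State that informant change from baseline is interpreted only as a difference between arms.

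The cost is an instruction sheet and a few sentences, with no added visit or staff. An unassisted baseline form may have a few more blank items. A small difference between site and home remains, which is why the analysis statements are needed as well. The plan should also say how much help the Veteran receives with the form, so that the two raters are comparable at baseline.

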2.0 Risks

We anticipate that this will be a study with minimal risk and low probability of adverse events. There may be some risk of emotional distress when subjects are completing self-report assessments; poor performance on neuropsychological tests may also cause distress. However, in the event that extreme distress is indicated by the study participant, that is, the study participant indicates that they wish to harm themselves or others, research staff will escort the participant to mental health intake. In the event of an adverse event it will be documented in the subject hard copy file and reported to the IRB within the time requirements set for by the local IRB and Office of Research Oversight.

Cognition and other Mental Health Behavioral Assessments:

Participant may experience some distress when completing self-report assessments or if they perform poorly on tests. Participants will be told they can decline to answer any question. They will also be told that some questions are meant to be hard and some are meant to be easy and we ask that they try their best. Screening assessments will take approximately 2-3 hours. At baseline, neuropsychological assessments will take approximately 90 minutes. For the end-point and follow-up, the battery will take approximately three hours to complete. Therefore, participants may experience fatigue. To address this burden, breaks will be encouraged and scheduled within the session. If a participant appears to be under undue strain, test sessions will be discontinued. The participants will be informed that at any point they can let the assessor know a break is requested.

Computer cognitive training intervention

Specific to intervention, several factors may contribute to non-compliance with program use. Several elements of flexibility will be incorporated in the treatment schedule to accommodate the challenges that Veterans with PD may encounter. First, the participant may require extra time to complete the program. Participants will be asked to engage in four 30-minute sessions per week for 8 weeks, which is 16 hours in total. Training progress and compliance will be automatically uploaded to a secure HIPAA-compliant server at Posit Science, and will be monitored weekly by the study staff. Note that participants will login to a web-based cognitive training program or gaming site using a number assigned to their loaned wireless equipped iPad, thus there is no PHI on this Posit Science server. If participants have completed less than 12 of the 16 hours of total training, then they will be allowed up to 4 additional weeks to complete the intervention. To ensure a time-bounded study commitment, after a total of 12 weeks such participants will perform their post-assessment (completion) visit regardless of the number of sessions completed. Second, we expect that not all participants will complete four sessions every week. To accommodate this, during the weekly phone calls to participants, the study team will work with them to generate a feasible training schedule if they are finding it difficult to meet requirements. Third, there may be some cases in which a participant may wish to stop or minimize the use of the program going forward, while remaining in the study. Potential reasons for this decision might be a change in health issues, family/personal issues or lack of interest in the intervention. However, the participant may want to meet their personal commitment to the basic scientific research of the study. In such cases, after a study team discussion with co-investigators, the participant will be permitted to cease using the program and be scheduled for a post-assessment (endpoint) visit at the appropriate time relative to the baseline assessment. If the participant completed at least 12 hours of training within 12 weeks, then a 1-month follow-up assessment will be scheduled. Fourth, some Veterans may not be able to complete the proposed training regimen in one sitting (i.e., 30 minutes) due to fatigue. To accommodate this issue, participants may choose to break the time into shorter segments, which are more easily manageable.

Confidentiality:

Loss of confidentiality is a potential risk. This research study involves collection of questionnaires. To protect from breach of confidentiality, each participant will be assigned a unique identification number by the study personnel and the only place where this participant identification number will be linked to identifying information (e.g., name, address, phone number, date of birth, social security number) will be on a cross-walk

file within secure Hines VA servers. [name] will provide limited access to the data. Hard copies of questionnaires response forms will be kept in a lockable file cabinet in a lockable office of [name] at Hines VAH. Any breach in security will be reported to ACOS/Research, Facility Information Security Officer (ISO) and facility Privacy Officer within one hour. All Hines data will remain at Hines and will not be taken off station. No data will be stored on hard drives.

Unknown cognitive training Risks:

There may be other unforeseeable and/or unanticipated side effects that could occur. An adverse events (AE) log and weekly study monitor log will be used to monitor the occurrence of any AE including unanticipated events. A response plan to unanticipated AE will be developed should this occur.

